In addition, antacid preparations containing magnesium trisilicate are prohibited from the start of study treatment at the Baseline Visit throughout the completion of the dosing period (i.e., until all 10 doses of study treatment have been received).

Due to the gepotidacin’s property of acetylcholinesterase inhibition, the concomitant use of succinylcholine or other nondepolarizing paralytic agents is also prohibited. Caution should be used in participants who have a condition requiring medication that may exacerbate the inhibition of acetylcholinesterase, or neuromuscular blocking agents.

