8. STUDY ASSESSMENTS AND PROCEDURES

- Study procedures and their timing are summarized in the SoA (Section 1.3).
- Protocol waivers or exemptions are not allowed.
- Immediate safety concerns should be discussed with the sponsor immediately upon occurrence or awareness to determine if the participant should continue or discontinue study treatment.
- Adherence to the study design requirements, including those specified in the SoA, is essential and required for study conduct.
- All baseline screening evaluations must be completed and reviewed to confirm that potential participants meet all eligibility criteria. The investigator will maintain a

screening log to record details of all participants screened and to confirm eligibility or record reasons for screening failure, as applicable.

- Procedures conducted as part of the participant's routine clinical management (e.g., blood count) and obtained before signing of ICF may be utilized for screening or baseline purposes provided the procedure met the protocol-specified criteria and was performed within the time frame defined in the SoA.
- Prescreening activities may be conducted, including a prescreening informed consent and urine testing, as further detailed in the SRM. The required baseline urine specimen may be collected as part of an optional prescreening process, if not already part of standard of care, and is further detailed in the SRM. This specimen can be used for the required baseline procedures of the diagnosis of presumptive acute cystitis and pregnancy testing.
- The maximum amount of blood collected from each participant over the duration of the study, including any extra assessments that may be required, will not exceed 200 mL.
- Repeat or unscheduled samples may be taken for safety reasons or for technical issues with the samples.
- Participants may return to the study site at any time due to AEs or if they are experiencing new or continuing signs and symptoms of acute cystitis. Participants will be assessed and treated per the investigator's judgement. If a participant is switched to a different antibiotic before or during the TOC Visit, all TOC procedures should be completed before the other antibiotic is started.
- Each treatment day will be assessed over 24 hours starting with the first dose of study treatment, as further detailed in the SRM.

The study will comprise the following 4 planned study visits:

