
Microbiologically Evaluable at TOC (ME-TOC) Population
	
 Participants who meet the definition of the micro-ITT Population, follow important components of the study (i.e., (1) receive at least 80% of planned doses as randomized and actual treatment received is the same as randomized, (2) have an interpretable quantitative urine culture at the TOC Visit and evaluable clinical scores at the baseline and the TOC Visit, (3) have not taken any other systemic antimicrobial before TOC unless it was taken for the current infection, and (4) have no other major protocol deviation that prevents evaluation of efficacy. Participants will be analyzed according to their randomized study treatment, however, by definition, for all participants in this analysis population the actual treatment received is the same as randomized. 	
 Efficacy

Microbiologically Evaluable at FU (ME-FU) Population
	
 Participants who meet the definition of the micro-ITT Population, follow important components of the study (i.e., (1) receive at least 80% of planned doses as randomized and actual treatment received is the same as randomized, (2) have an interpretable quantitative urine culture at FU Visit (unless microbiological outcome at TOC is persistence or recurrence) and evaluable clinical scores at the baseline and the FU Visit (unless clinical outcome at TOC is clinical improvement or worsening), (3) have not taken any other systemic antimicrobial 	
 Efficacy

Population	Definition / Criteria	Analyses Evaluated
	
before FU unless it was taken for the current infection (therapeutic failure), and (4) have no other major protocol deviation that prevents evaluation of efficacy.
 
 Participants will be analyzed according to their randomized study treatment, however, by definition, for all participants in this analysis population the actual treatment received is the same as randomized. 	
ME-OT NTF-S Population	
 All participants in the ME-OT Population whose baseline qualifying uropathogens are all susceptible to nitrofurantoin. Participants will be analyzed according to their randomized study treatment, however, by definition, for all participants in this analysis population the actual treatment received is the same as randomized. 	
 Efficacy

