Clinically Evaluable at OT (CE-OT) Population	
 • All participants in the ITT Population who follow important components of the study as specified in the protocol (i.e., (1) receive at least 80% of planned doses as randomized and actual treatment received is the same as randomized, (2) have evaluable clinical scores of signs and symptoms at the baseline and the OT Visit, (3) have not received other systemic antimicrobials before OT unless it was for the current infection (therapeutic failure), and (4) have no other major protocol deviation that prevents evaluation of efficacy). • Participants will be analyzed according to their randomized study treatment, however, by definition, for all participants in this analysis population the actual treatment received is the same as randomized. 	
 • Efficacy
Clinically Evaluable at TOC (CE-TOC) Population	
 • All participants in the ITT Population who follow important components of the study as specified in the protocol (i.e., (1) receive at least 80% of planned doses as randomized and actual treatment received is the same as randomized, (2) have evaluable clinical scores of signs and symptoms at the baseline and the TOC Visits, (3) have not received other systemic antimicrobials before TOC unless it was for the current infection (therapeutic failure), and (4) have no other major protocol deviation that prevents evaluation of efficacy. • Participants will be analyzed according to their randomized study treatment, however, by definition, for all participants in this analysis population the actual treatment received is the same as randomized. 	
 • Study Population • Efficacy
Clinically Evaluable at FU (CE-FU) Population	
 • All participants in the ITT Population who follow important components of the study as specified in the protocol (i.e., (1) receive at least 80% of planned doses as randomized and actual treatment received is the same as randomized, (2) have evaluable clinical scores of signs and symptoms at the baseline and the FU Visit (unless clinical outcome at TOC is clinical 	
 • Efficacy

Population	Definition / Criteria	Analyses Evaluated

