5.6. Analysis Visits

Analysis visit windows will be defined for by-visit summary and analysis purposes as illustrated in Table 5. Data not reported by-visit, including adverse events and concomitant medications, will not employ analysis visits. Analysis visit labels will be assigned to each post-baseline record (including records from unscheduled and early termination visits) based on the corresponding study day (relative to first study treatment or randomization if not treated). For post-baseline records collected outside the analysis visit window, a blank analysis visit label will be assigned. For example, a record collected at study Day 6 will not be utilized in any analyses or by visit descriptive summaries conducted at the OT or TOC scheduled visit. Descriptive summaries that are shown for “any assessment post baseline” e.g. maximum/minimum/ worst case post baseline, will use all assessments irrespective of whether they fall in an analysis visit window.

Table 5 Analysis Visit Windows

Post-Baseline Scheduled Visit	Protocol Window (Days)	Target Day	Analysis Visit Window (Days)
On-therapy	2 to 4	3	2 to 5

Post-Baseline Scheduled Visit	Protocol Window (Days)	Target Day	Analysis Visit Window (Days)
Test-of-Cure	10 to 13	12	9 to 16
Follow-up	25 to 31	28	21 to 31

If multiple records exist within the same analysis visit window, then the record occurring closest to the target day will be utilized in all analyses and analysis population determinations. If multiple records are equally close to the target day, then the later record will be utilized. If multiple records occur on the same day and time is not collected, then the record with the larger Study Data Tabulation Model (SDTM) record sequence number will be utilized in all analyses. All protocol assessments (including unscheduled and early termination visits) will be presented in subject Listings. Both the nominal and analysis visit will be presented in Listings.

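### The evaluable (ME and CE) populations drop participants who failed early and were rescued, although one of their own clauses is written to keep them as failures

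*SAP*

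**What the plan says.** Each visit-level ME and CE definition in SAP Section 4 has four numbered clauses. Three matter here.

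- **Clause (1), dosing**, identical in all six definitions: "receive at least 80% of planned doses as randomized and actual treatment received is the same as randomized". Protocol 6.5.2 fixes the full course ("until all 10 doses of study treatment have been received").
- **Clause (2), visit data.** ME-TOC participants must "have an interpretable quantitative urine culture at the TOC Visit and evaluable clinical scores at the baseline and the TOC Visit". CE-TOC participants must "have evaluable clinical scores of signs and symptoms at the baseline and the TOC Visits". Neither has a waiver. ME-FU waives the Follow-up culture after persistence or recurrence at TOC. ME-FU and CE-FU waive the Follow-up score after clinical improvement or worsening at TOC.
- **Clause (3), other antimicrobials.** ME-TOC participants must "have not taken any other systemic antimicrobial before TOC unless it was taken for the current infection". CE-TOC has the same carve-out and labels these participants: "have not received other systemic antimicrobials before TOC unless it was for the current infection (therapeutic failure)".

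Two further provisions bear on clause (2). For a participant who is switched before or at TOC, Protocol 8 says "all TOC procedures should be completed before the other antibiotic is started". SAP 5.6 sets the TOC analysis window at Days 9 to 16 and leaves records between windows unlabelled: "a record collected at study Day 6 will not be utilized in any analyses" tied to the On-therapy or TOC visit.

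**The concern.** Clause (3) shows the intent: rescue for the infection under study is an efficacy outcome, and those participants belong in the evaluable set as failures. Clauses (1) and (2) then remove many of them. Stopping early for lack of efficacy is foreseen in Protocol 7.1, which lists it as a discontinuation reason and lets the investigator start alternative therapy.

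Everyone lost by this route is a failure, so this is selection on outcome. An evaluable-population analysis is commonly read beside the ITT-type analysis in a non-inferiority trial as a check on dilution. A set that has shed known failures is a weaker check. Both arms look better than they did, and the difference can move either way if early rescue is unbalanced.

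**Working it through.** **1. The plan's own figures.** The documents give no size, power or exclusion rate for ME or CE. The nearest stated figures are for the primary population, and they reproduce at 76% in both arms, margin -10% and one-sided 0.025. Group-sequential power at 884 with the SAP Table 2 boundaries is 90.2% (stated: about 90%). Futility-only power at 768 is 88.4% (stated: about 88%). None of this depends on the ME or CE rules.

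**2. Where clause (1) bites.** 0.80 × 10 doses = 8 doses. At 12-hour intervals, dose 8 falls 7 × 12 = 84 hours after the first, in treatment Day 4. A participant switched before then fails clause (1), even though clause (3) would retain her. In ME-OT and CE-OT the carve-out is nearly empty: someone switched before an On-therapy visit on Days 2 to 4 can hardly have taken 8 doses. Those visits carry outcome categories only, with no success/failure response, so the consequence for response rates lies at TOC and Follow-up.

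**3. Where clause (2) bites.** A participant may complete dosing, have her TOC procedures on Days 6 to 8 as Protocol 8 asks, and then start rescue. Those records carry no TOC label. If she does not return on Days 9 to 16, she fails clause (2).

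**4. The missing data are not needed.** SAP Table 8 makes rescue for the current infection, up to and including the TOC date, a clinical failure. SAP Table 6 makes any other systemic antimicrobial before TOC a microbiological failure. The SAP already uses this logic for the interim set, which admits participants not yet at TOC who are known failures.

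**5. The Follow-up gap.** Under SAP Table 6, a participant rescued before TOC has an undetermined microbiological outcome, neither persistence nor recurrence. The ME-FU culture waiver therefore misses her. The score waivers do cover her, because rescue for the current infection counts as clinical worsening.

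**6. Size, by illustration.** Let s be an arm's true success rate and x the share of that arm dropped as early rescued failures. The evaluable success rate is s/(1 - x). Take nitrofurantoin at 76% (the protocol's assumption) and gepotidacin at 66%, so the true difference sits at the margin. Start from 884/2 = 442 per arm. With d the evaluable difference and SE its Wald standard error from 442(1 - x) participants per arm, the chance that the lower 95% limit exceeds -10% is Φ((d + 0.10)/SE - 1.96). All values of x are assumptions.

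| x nitrofurantoin | x gepotidacin | Evaluable rates (NTF, GEP) | Difference (points) | Chance lower limit > -10% |
|---|---|---|---|---|
| 0% | 0% | 76.0%, 66.0% | -10.0 | 2.5% |
| 2% | 2% | 77.6%, 67.3% | -10.2 | 2.1% |
| 5% | 5% | 80.0%, 69.5% | -10.5 | 1.6% |
| 2% | 5% | 77.6%, 69.5% | -8.1 | 9.3% |
| 3% | 8% | 78.4%, 71.7% | -6.6 | 20% |
| 2% | 10% | 77.6%, 73.3% | -4.2 | 49% |
| 5% | 2% | 80.0%, 67.3% | -12.7 | 0.2% |

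For the 2%/5% row: 0.66/0.95 - 0.76/0.98 = 0.695 - 0.776 = -0.081. With 76% in both arms, dropping 5% from each gives 80.0% in both and a difference of 0.

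**The case against.** The best reply is that little rests on these populations. SAP 7.1.6.3 places ME-TOC among several supplementary analyses, reported as a difference with a 95% CI and no boundary test. CE supports the secondary clinical endpoints, which are descriptive. The primary micro-ITT NTF-S analysis counts rescued and missing participants as failures. That stands: alpha, power, sample size and the non-inferiority decision do not change.

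The visit-window loss is also conditional. Protocol 7.1 asks participants who stop treatment to attend all later visits, and SAP 5.6 labels any record from Days 9 to 16, scheduled or not. A participant rescued on Days 6 to 8 who then attends keeps her place under clause (2), and she may already have taken 8 doses. A reader might infer that following the protocol's switching instruction automatically removes a participant; the documents do not support that.

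A dose threshold is also what makes an evaluable set adherence-based, Protocol 7.1 expects permanent discontinuation to be rare, and SAP 6.1.1 tabulates reasons for exclusion by arm. These are fair points. However, tabulating exclusions does not restore the failures to the estimate, and a set meant to be purely adherence-based would have no use for clause (3).

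**Conclusion.** The clauses conflict, and the conflict removes known failures from the supplementary ME and descriptive CE analyses. The 80% rule has no failure exception in any of the six definitions. The TOC data rule has none in ME-TOC or CE-TOC, and ME-FU leaves a gap for participants rescued before TOC. This is worth correcting before unblinding.

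Three stronger readings are tempting and should not be adopted.

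- **That rescued failures are excluded outright.** Clause (3) is an explicit exception, and those rescued after 8 doses with in-window TOC data stay in.
- **That a key non-inferiority analysis is compromised.** The SAP applies that word to the CAPA and EU analyses, not to ME.
- **That the result is biased towards gepotidacin.** That happens only if early rescued failures are more frequent on gepotidacin, and no document gives these rates. Equal shares leave a zero difference at zero and slightly widen a negative one; the opposite imbalance works against gepotidacin.

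What can be said is that success rates are inflated in any arm with early rescued failures, and that the effect on the difference is unknown in direction and size. The table assumes that only these failures are dropped. Clause (1) also removes participants who stopped for adverse events and non-adherent successes, which would alter the figures.

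**What to change.** Reconcile the clauses in SAP Section 4.

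- **Clause (1), all ME and CE definitions:** exempt a participant who is already a failure through a systemic antimicrobial for the current infection, subject to a minimum exposure that the sponsor sets and justifies before unblinding. The documents offer no basis for a particular number of doses. This would be a criterion for analysis only.
- **Clause (2), TOC and Follow-up definitions:** exempt the same participants from the post-baseline culture and score requirement, and count them as failures. Keep the baseline score requirement. Covering Follow-up closes the ME-FU culture gap.
- **SAP 2.1:** list the change. Protocol 9.3 requires an interpretable culture at the visit for ME, so the waiver departs from the protocol.

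If the sponsor prefers to exclude these participants, the SAP should justify that and report by arm how many rescued failures were removed.

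The cost is SAP wording, one derived flag and an entry in SAP 2.1. Section 4 settles population membership before unblinding, so the change fits the existing process. The downside is that ME and CE success rates will be slightly lower.

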(1) The TOC urine culture result is missing or (2) The participant received other systemic antimicrobials before the TOC Visit	Unable to determine	Microbiological failure

CFU=colony-forming units; TOC=Test-of-Cure.

Table 7 Participant-level microbiological outcome and response at the TOC Visit

Defining Criteria	Outcome	Response
All qualifying baseline uropathogens have a microbiological outcome of eradication at TOC	Microbiological eradication	Microbiological success
At least one qualifying baseline uropathogen has an outcome of persistence at TOC	Microbiological persistence	Microbiological failure
At least one qualifying baseline uropathogen has an outcome of recurrence and none have an outcome of persistence at TOC	Microbiological recurrence	Microbiological failure
All qualifying baseline uropathogen outcomes are unable to determine at TOC	Unable to determine	Microbiological failure

TOC=Test of Cure

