(1) The baseline score is missing or (2) The TOC assessment is missing or (3) The participant received other systemic antimicrobials not for the current infection before the TOC Visit (unless clinical worsening outcome criteria were met)	Unable to determine	Clinical failure

TOC=Test-of-Cure.

If participant took both other systemic antimicrobials for the current infection on or before the date of the TOC Visit (started on/after Study Day 1), and other systemic antimicrobials not for the current infection before the date of the TOC Visit (started on/after Study Day 1), then participant will be derived as ‘Clinical worsening’.

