7.2.1. Endpoint / Variables

7.2.1.1. Microbiological Outcome and Response at TOC and Follow-up

The microbiological outcome and response are evaluated at participant level at the TOC and FU Visits. The criteria of uropathogen-level microbiological outcome and response are defined in Table 6 (TOC) and similarly in Table 9 (FU). The criteria of participant-level microbiological outcome and response are defined in Table 7 (TOC) and Table 10 (FU).

Table 9 Microbiological Outcome and Response by Baseline Qualifying Uropathogen at the Follow-Up Visit – Uropathogen Level

Defining Criteria	Outcome	Response
Participants considered microbiological failures at the TOC Visit will also be considered microbiological failures at the FU Visit.		
A quantitative urine culture taken at the Follow-up Visit shows reduction of the qualifying uropathogen recovered at Baseline to $<10^3$ CFU/mL following microbiological eradication at the TOC Visit, without the participant receiving other systemic antimicrobials before the Follow-up Visit	Sustained microbiological eradication	Microbiological success
A quantitative urine culture taken at the Follow-up Visit shows that the qualifying uropathogen recovered at Baseline grows $\geq 10^3$ CFU/mL following microbiological eradication at the TOC Visit, without the participant receiving other systemic antimicrobials before the Follow-up Visit	Microbiological recurrence	Microbiological failure
A quantitative urine culture taken at the Follow-up Visit shows that the qualifying uropathogen recovered at Baseline grows $\geq 10^3$ CFU/mL, and also did not achieve an outcome of microbiological eradication at the TOC Visit, without the participant receiving other systemic antimicrobials before the Follow-up Visit	Microbiological persistence	Microbiological failure
A quantitative urine culture taken at the Follow-up Visit shows reduction of the qualifying uropathogen recovered at Baseline to $<10^3$ CFU/mL, and also did not achieve an outcome of microbiological eradication at the TOC Visit, without the participant receiving other systemic antimicrobials before the Follow-up Visit	Delayed microbiological eradication	Microbiological failure
1) The FU urine culture result is missing or 2) The participant received other systemic antimicrobials before the FU Visit	Unable to determine	Microbiological failure

CFU=colony-forming units; TOC=Test-of-Cure.

Table 10 Participant-Level Microbiological Outcome and Response at the Follow-Up Visit

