7.2.1.2. Clinical Outcome and Response at TOC and Follow-Up

Clinical outcome and response are evaluated at participant level at the TOC and FU Visits. The criteria for clinical outcome and response are defined in [Table 8](#) (TOC) and similarly in [Table 11](#) (FU).

Table 11 Clinical Outcome and Response at the Follow-Up Visit

Defining Criteria	Outcome	Response
Participants who withdraw from the study prior to the FU Visit will be considered not achieving success (imputed as failure) as the clinical response at FU.		
Resolution of signs and symptoms of acute cystitis demonstrated at the TOC Visit persist at the FU Visit (and no new signs and symptoms), without the participant receiving other systemic antimicrobials before the FU Visit.	Sustained clinical resolution	Clinical success
Resolution of signs and symptoms of acute cystitis present at Baseline (and no new signs or symptoms), after clinical failure at TOC, without the participant receiving other systemic antimicrobials before the FU Visit.	Delayed clinical resolution	Clinical failure
Improvement in total symptom scores from Baseline, but not complete resolution, without the participant receiving other systemic antimicrobials before the FU Visit.	Clinical improvement	Clinical failure
Worsening or no change in total symptom scores at FU compared to Baseline after clinical failure at TOC or the participant received other systemic antimicrobials for the current infection before or on the date of the FU Visit	Clinical worsening	Clinical failure
Signs and symptoms of acute cystitis reoccur at the FU Visit assessment after clinical success at the TOC Visit	Clinical recurrence	Clinical failure
1) The baseline score is missing or 2) The FU assessment is missing or 3) The participant received other systemic antimicrobials not for the current infection before the FU Visit (unless clinical worsening or recurrence outcome criteria were met)	Unable to determine	Clinical failure

TOC=Test-of-Cure. FU=Follow-up.

If participant took both other systemic antimicrobials for the current infection on or before the date of the FU Visit, and other systemic antimicrobials not for the current infection before the date of the FU Visit, then participant outcome will be derived as ‘Clinical worsening’.

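### The evaluable-at-Follow-up populations (ME-FU, CE-FU) do not require a TOC result, so a participant with missing TOC data who is clear at Follow-up is kept and scored a failure

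*SAP*

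**What the plan says.** SAP section 4 sets different entry rules for the evaluable populations at the two visits. For ME-TOC a participant must "have an interpretable quantitative urine culture at the TOC Visit and evaluable clinical scores at the baseline and the TOC Visit", and CE-TOC likewise needs a TOC score. ME-FU drops the TOC data: participants must "have an interpretable quantitative urine culture at FU Visit (unless microbiological outcome at TOC is persistence or recurrence"), and the clinical requirement is "evaluable clinical scores at the baseline and the FU Visit (unless clinical outcome at TOC is clinical improvement or worsening"). CE-FU asks that they "have evaluable clinical scores of signs and symptoms at the baseline and the FU Visit (unless clinical outcome at TOC is clinical" improvement or worsening). Follow-up data are thus needed unless TOC already showed a failure, and no TOC result is needed at all.

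The scoring tables do depend on TOC:

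- **Table 6** gives *unable to determine*, scored as microbiological failure, when "The TOC urine culture result is missing or (2) The participant received other systemic antimicrobials before the TOC Visit".
- **Table 8** does the same for clinical response; one listed reason is "The TOC assessment is missing".
- **Table 9** opens with the rule "Participants considered microbiological failures at the TOC Visit will also be considered microbiological failures at the FU Visit". Its only success category requires eradication at TOC.
- **Table 11** has one success category, which requires resolution already shown at TOC. Its row "Resolution of signs and symptoms of acute cystitis present at Baseline (and no new signs or symptoms), after clinical failure at TOC" is labelled delayed clinical resolution and counts as failure.

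Protocol Tables 4 and 11 have the same structure. SAP 7.2.6.3 uses ME-FU for supplementary analyses of therapeutic and microbiological response and CE-FU for clinical response. SAP 7.2.6.1 says that secondary endpoints are not formally tested.

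**The concern.** Entry to the Follow-up sets and scoring within them do not match. Success has to be sustained from TOC, but a participant can enter with nothing recorded at TOC. She then cannot succeed, whatever Follow-up shows. Attending Follow-up with a clean result counts against her arm, while staying away does not.

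The SAP itself creates several routes to a missing TOC result. A visit on Days 17 to 20 falls between the TOC analysis window (Days 9 to 16) and the Follow-up window (Days 21 to 31) in SAP Table 5. An out-of-stability urine sample is dropped from analysis (SAP 11.4.4). One missing symptom item makes the total score missing (SAP 7.1.1.3).

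At stake is how far the ME-FU and CE-FU results can be read as what happened to participants with usable data. No other planned Follow-up analysis makes up for this. The missing-at-random imputation in SAP 7.1.6.2 covers only the primary TOC endpoint, and the sensitivity analyses of secondary endpoints (SAP 7.2.6.2) are unadjusted differences.

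**Working it through.** The plan states no figure for this point, so there is nothing to reproduce. The check has two parts.

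**1. Tracing the rules.** Assume at least 80% of doses taken, no other antimicrobials and no other exclusion. Apply SAP section 4 and Tables 6, 8, 9 and 11 literally to a participant whose Follow-up culture is below 10^3 CFU/mL and whose Follow-up score is 0, unless the row says otherwise:

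| TOC culture | TOC score | ME-TOC | ME-FU | CE-FU | Follow-up microbiological | Follow-up clinical | Therapeutic |
|---|---|---|---|---|---|---|---|
| missing | missing | out | in | in | delayed eradication, failure | delayed resolution, failure | failure |
| missing | 0 | out | in | in | delayed eradication, failure | sustained resolution, success | failure |
| negative | missing | out | in | in | sustained eradication, success | delayed resolution, failure | failure |
| missing | missing, and Follow-up also missing | out | out | out | n/a | n/a | n/a |

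No one with a missing TOC culture can be a microbiological success at Follow-up. No one with a missing TOC score can be a clinical success. Either gap alone makes the therapeutic response a failure.

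**2. Size.** Let m be the share of the Follow-up set with a missing TOC component and no observed TOC failure. Let p be the success rate in the rest of the set. Then the reported rate is p(1 − m), and the understatement is p × m.

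Both inputs are assumptions. For p the range is 60% to 76%: the lowest and highest success rates in the planning tables of Protocol 9.2.2. The Phase IIa Follow-up therapeutic result, 5/8 = 63% (Protocol 2.1), lies inside it. For m the range is 2% to 10%.

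| p | m = 2% | m = 5% | m = 10% |
|---|---|---|---|
| 60% | 58.8% (−1.2) | 57.0% (−3.0) | 54.0% (−6.0) |
| 70% | 68.6% (−1.4) | 66.5% (−3.5) | 63.0% (−7.0) |
| 76% | 74.5% (−1.5) | 72.2% (−3.8) | 68.4% (−7.6) |

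With the same m in both arms, a true difference D is reported as D(1 − m), that is 0.98D, 0.95D or 0.90D.

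With equal true rates but unequal missingness, the false difference is p × (m₁ − m₂), against the arm with more missing TOC results:

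- 5% v 2%: 0.60 × 3 = 1.8 points to 0.76 × 3 = 2.3 points.
- 10% v 2%: 0.60 × 8 = 4.8 points to 0.76 × 8 = 6.1 points.

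**The case against.** **The endpoint comes from the protocol.** Protocol Tables 4 and 11 define Follow-up success as sustained and carry TOC failures forward; the SAP follows them. That stands, and it is a reason to leave the response definition alone. It does not settle who belongs in an evaluable set: Protocol 9.3 leaves the visit-specific ME and CE definitions to the analysis plan.

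**The labels follow a convention.** Table 9 defines delayed eradication by the absence of eradication at TOC; it does not say that infection was seen there. A reader might also infer that *persistence* is wrong for Follow-up growth after a missing TOC. The documents do not support that. Table 6 openly uses the same convention one visit earlier, where TOC growth after an undetermined On-therapy result is called persistence.

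**There is an exclusion route.** Criterion (4) removes participants with another major deviation that prevents evaluation of efficacy, as decided by the study team before database lock. A missed or late TOC visit might be handled there. The text does not name it, however, and the criterion would not clearly reach an out-of-stability sample or a single missing symptom item.

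**Intent.** A reader might infer from the waivers that only observed TOC failures were meant to carry forward. The waivers say only when Follow-up data may be absent; the Table 9 rule covers every TOC microbiological failure. Nor does either document say that the evaluable sets exist to avoid counting missing data as failure. The point rests on the mismatch between entry and scoring.

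**Conclusion.** The point holds on the text. Followed as written, the plan gives biased ME-FU and CE-FU results: success is understated by about 1 to 8 points for 2% to 10% missing TOC, and differences shrink by the factor (1 − m). Unequal missingness shows up as a treatment difference of about 2 points at 5% v 2%. These sizes depend on assumed values of m and p, and on the study team not removing such participants under criterion (4).

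The reach is limited. The analyses are supplementary and descriptive. The primary TOC analysis in micro-ITT NTF-S does not use these sets, and scoring missing data as failure is the stated rule in the ITT-type populations. A reader might set the distortion against the 10-point noninferiority margin; the documents give no basis for that, because the margin belongs to the primary TOC test only.

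**What to change.** **1. Population rule (recommended).** In ME-FU, its NTF-S and NTF-NS derivatives, and CE-FU, add a requirement for a non-missing TOC culture and TOC clinical score (for CE-FU, the clinical score only). Apply it whatever the Follow-up result, because removing only those who were clear at Follow-up would bias the rate the other way. Make one exception: a participant with an observed TOC failure on either component stays in as a failure. Observed failure means persistence, recurrence, clinical improvement, or clinical worsening, including antimicrobials for the current infection on or before the TOC date. For CE-FU only the clinical component is relevant.

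The cost is one SAP sentence and one programming condition, settled with the population determination before unblinding. A few participants leave these supplementary sets, including some who failed at Follow-up. One residue remains: someone kept in ME-FU for an observed clinical failure, with no TOC culture, still counts as a microbiological failure there. Her therapeutic failure is genuine.

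**2. Labels (optional).** In SAP Tables 9 and 11, when TOC is missing and Follow-up is negative or resolved, report the Follow-up outcome as *unable to determine* (TOC missing) instead of *delayed*. Leave the response as failure in the ITT-type populations, and list the change in SAP 2.1 as a departure from Protocol Tables 4 and 11. Keep the existing labels for documented Follow-up growth, continuing symptoms and rescue.
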